5. STUDY OUTCOMES

5.1 Primary Outcome

The FNA material of lymph node tissue at baseline and 2, 6 or 24 hours after allergen injection (via ILIT or SCIT) will be evaluated for changes in cellular composition and functions.

Immunological changes in peripheral blood at baseline, after 2, 6 or 24 hours, after 7 days and after 28 days of allergen ILIT or SCIT will be analysed by measuring cellular composition and functions in whole blood and in culture blood cells as well as inflammatory proteins and antibodies in serum.

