7. STUDY POPULATION

7.1 Eligibility criteria

Participants fulfilling all of the following inclusion criteria are eligible for the study:

- Patients who have seasonal grass-pollen-induced rhinoconjunctivitis as confirmed by patient history and type-1-sensitization to grass-pollen in skin and/or serum
- Patients that undergo pre-seasonal short-term scheme with Polvac™ SCIT at the USZ Allergy Unit in autumn and winter 2023 for treatment of allergic rhinoconjunctivitis.
- Informed Consent as documented by signature.
- Patients are between 18 and 55 years of age when they sign the informed consent.

The presence of any one of the following exclusion criteria will disqualify the patient from participating the study:

Allergy related exclusion criteria:

- Known or suspected allergy to additives to the study product
- Known intolerance or allergy to phenol
- Planned depot steroid injection for treatment of allergic rhinoconjunctivitis
- Uncontrolled asthma or severe asthma with post bronchodilator $FEV1 < 70\%$, decided by the investigator
- Pulmonary disease with post bronchodilator $FEV1 < 70\%$ of predicted
- Pulmonary disease, perennial or seasonal, with daily use of more than 800 microgram inhaled budesonide/day (or equivalent)
- Treatment with omalizumab or other biologics for allergy, AD, urticaria or asthma.
- Allergic reaction within the last 4 days or anaphylaxis within last month before planned ILIT or SCIT injection.

Exclusion criteria based on serious comorbidities as judged by the recruiting physician:

- Autoimmune or collagen disease
- Disease or conditions rendering the treatment of anaphylactic reactions difficult (symptomatic coronary heart diseases, severe arterial hypertension, and treatment with beta-blockers)
- Concomitant infection with fever or other signs/symptoms of an acute or chronic infection at treatment visit
- Vaccination of any kind two weeks before or after the ILIT or SCIT injections.
- Known cardiovascular disease, i.e., not even NYHA class I.
- Use of ACE-blockers.
- Recent or on-going hepatic or renal disease
- Any malignant disease
- Conspicuous lymph node size or morphology
- Immuno- or chemotherapy during the last 15 years.
- Increased bleeding tendency
- Any other than study medication with an effect of interfering with the immune response
- Chronic obstructive or restrictive lung disease
- Skin diseases with barrier defect in the inguinal areas
- Alcohol or drug abuse
- Women who are pregnant and breast feeding

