7.2 Recruitment and screening

We will recruit 30 patients directly at the USZ Allergy Unit. All 30 participants must have a type-1-sensitisation to grass pollen allergens and be undergoing pre-seasonal short-term SCIT scheme with Polvac™ at the USZ Allergy Unit in winter 2023/2024.

Patients will be invited to a screening visit 1 to 60 days before the intervention, where an extensive interview will be conducted and the informed consent will be signed by the patient and the medical investigator. The informed consent will be uploaded to the clinical information system (KISIM) and filed

into the trial master file (TMF). At the screening visit there will be a medical interview assessing all inclusion and exclusion criteria and a short clinical exam (auscultation of the lungs and the heart, blood pressure measurement).

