8.6 Trial specific preventive measures

All the preventive measures described below will be recorded in the CRF.

Prior to the allergen injection, a pregnancy testing (if applicable) will be performed.

The patients will receive an emergency set ("Allergie Notfallset") to take home in case of systemic side effects (Appendix 003). The emergency set consists of two tablets of Xyzal® 5 mg (Levocetirizine dihydrochloride) and two tablets of Spiricort® 50 mg (Prednisolone). Patients will be given an instruction about when and how to use the emergency set. Fenistil gel 1% will be given for local allergic reactions restricted to the site of injection.

After ILIT treatment the patients have to stay one hour at the allergy unit for observation.

During the study (from allergen injection to blood samplings after 28 d) patients cannot receive another allergen injection. To avoid allergen exposure from the environment, the study allergen is seasonal, and therefore not in the environment during the whole study period.

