9.2.1.3 Analysis of T-cell activation by flow cytometry

PBMCs are also analyzed by flow cytometry after allergen-restimulation in vitro. Briefly, the cells are typically cultured 18-20h in the presence of grass pollen allergens, the last 4-6 hours of the incubation, the compound brefeldin A is added to prevent the golgii apparatus to release newly produced proteins. Then, the cell are stained for with fluorescent antibodies to detect lymphocytes, lymphocyte activation surface proteins. The cell are then fixed, permeabilised and stained to detect intracellular transcription factors such as Foxp3, STAT-1 and STAT-3 and STAT-6 as well as intracellular cytokines such as IL-4, IL-10 and IFN-gamma. The exact cytokines may depend on the result from the above-mentioned ELISA

studies. The cells are acquired on a BD LSR-Fortessa Cell analyzer and the data analyzed using FlowJo LCC software.

[figure not shown]

Figure 4. Patient flow chart illustrating study visits with timing, interventions, and assessments for patients treated by ILIT or SCIT for grass pollen-mediated allergic rhinoconjunctivitis.

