9.2.1.4 Multiparameter cellular analysis by mass cytometry (CyTOF)

PBMCs as well as lymph node cells are also analyzed by mass spectrum cytometry (45, 46) Again, cryotubes are thawed and cell immediately washed with complete medium. The cells are incubated with a viability dye washed extensively, and stained for a wide panel of extracellular antigens that will enable us to detect the phenotype of all possible leucocytes. After fixation and permeabilisation, the cells are patient-wise barcoded using the commercial Barcoding Kit (Fluidigm) and pooled before staining for intracellular antigens. Cell DNA is then stained using Cell-ID™ Intercalator-Ir (Fluidigm) overnight at 4°C, frozen at -80°C using a cryopreservation box, thawed, supplemented with Four Element Calibration Beads (Fluidigm) and acquired on a Helios™ mass cytometer. Files are concatenated, normalized, and debarcoded using the CyTOF software v6.7.1014. The data are analyzed by descriptive statistics as well as multivariate test methods with dimension reduction, e.g. PCA, t-SNE and UMAP (47).

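### The vaccination bar in 7.1 ends on day 14, so a vaccine on days 15-27 is not clearly excluded before the day-28 blood draw, which is part of the primary outcome

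*Combined protocol and SAP*

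**What the plan says.** Section 7.1 of the combined protocol and SAP lists as an exclusion criterion "Vaccination of any kind two weeks before or after the ILIT or SCIT injections". It is the only rule that names vaccines. A separate line in 7.1 excludes "Any other than study medication with an effect of interfering with the immune response", with no time window and no mention of vaccines.

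Section 5.1 includes in the primary outcome peripheral blood "after 7 days and after 28 days of allergen ILIT or SCIT", covering cell composition and function as well as "inflammatory proteins and antibodies in serum". Sections 8.2.1.3 and 9.3.5 confirm the day-28 draw.

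On timing and enforcement:

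- Section 7.2: "At the screening visit there will be a medical interview assessing all inclusion and exclusion criteria".
- Section 8.6: "During the study (from allergen injection to blood samplings after 28 d) patients cannot receive another allergen injection".
- Section 8.7, on concomitant interventions, lists study procedures and sets no vaccination rule.
- Table 1 marks a concomitant-medication check at Visit 5 (day 28).
- Section 11.5 commits to leaving no data unused.

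**The concern.** The study describes what one ILIT or SCIT injection does to the immune system. A vaccine is a second immune stimulus. The existing rule gives the baseline draw two vaccine-free weeks, but the two weeks before the day-28 draw have no such protection. Section 11.4 allows paired tests of change over time, so a protected baseline may be compared with an unprotected day-28 sample.

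The exposure differs by assay:

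- **Most exposed:** mass cytometry, which stains a "wide panel of extracellular antigens that will enable us to detect the phenotype of all possible leucocytes" (9.2.1.4), and any serum inflammatory proteins measured under 5.1. Neither is specific to grass pollen, so a vaccine response could be taken for a late effect of the study injection.
- **Little exposed:** the ImmunoCAP antibodies, which are grass-pollen specific (9.2.1.1), and the ELISA, ELISPOT and flow cytometry readouts, which depend on allergen restimulation. For flow cytometry, for example, "the cells are typically cultured 18-20h in the presence of grass pollen allergens" (9.2.1.3).

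At stake is avoidable noise at one blood time point, in a study with 15 patients per arm.

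**Working it through.** The plan states no figure on this point to reproduce. The check is day arithmetic, followed by a sizing on assumed inputs.

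**1. The gap.** The bar ends on day 14 (7.1) and the last primary-outcome draw is on day 28 (5.1). Days 15 to 27 are 27 − 15 + 1 = 13 days. The aspirates, the 2/6/24-hour blood and the day-7 blood all fall inside the barred period.

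**2. How often.** The documents give n = 30 and no vaccination rate. Assume r = 0.25, 0.5 or 1 vaccination per person-year, spread evenly over the year. Then p = r × 13/365, the expected number is 30p, and the chance of at least one is 1 − (1 − p)^30.

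| r per year | p | Expected among 30 | Chance of at least one |
|---|---|---|---|
| 0.25 | 0.0089 | 0.27 | 23.5% |
| 0.5 | 0.0178 | 0.53 | 41.7% |
| 1 | 0.0356 | 1.07 | 66.3% |

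These figures follow the assumption. If instead 2%, 5% or 10% of patients were vaccinated in the gap, the expected number would be 0.6, 1.5 or 3, and the chance of at least one 45%, 79% or 96%.

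**3. Effect if it happens once.** Assume one patient in an arm of 15 is shifted by k = 1, 2 or 3 SD on some readout, with no vaccinated patient in the other arm. The arm mean, and so the between-arm difference, moves by k/15. The standard error of a difference between two 15-patient means is √(2/15) = 0.365 SD. The arm's expected variance becomes 1 + k²/15. The median shift was simulated with 400,000 normal samples of 15.

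| k | Shift in mean difference (SD) | As share of SE | Arm SD inflated by | Shift in median (SD) |
|---|---|---|---|---|
| 1 | 0.067 | 18% | 3% | 0.06 |
| 2 | 0.133 | 37% | 12.5% | 0.08 |
| 3 | 0.200 | 55% | 26% | 0.09 |

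**4. Effect averaged over how often it happens.** If each patient independently has probability p of a k-SD shift, the per-patient variance becomes 1 + p(1 − p)k², and the standard error of the difference grows by the factor √(1 + p(1 − p)k²).

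- p = 0.0089, k = 1: √1.0088 = 1.004, a rise of 0.4%.
- p = 0.0178, k = 2: √1.0700 = 1.034, a rise of 3.4%.
- p = 0.0356, k = 3: √1.309 = 1.144, a rise of 14%.

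**5. With the bar extended to the day-28 draw**, the uncovered days fall from 13 to 0.

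**The case against.** The length of a vaccination window is a design choice, and nothing in the plan says the bar was meant to protect every later draw. The general line on medication that interferes with the immune response has no end date and could be read as covering the whole study. The screening interview already has to raise vaccination after the injection, and the Visit 5 check could record a vaccine. The rate and the shift are assumed. At the two lower rates the most likely outcome is no vaccinated patient at all (76.5% and 58.3%), and step 3 describes only the case where exactly one occurs. It also gives a vaccine on day 15 the same effect as one on day 27. Finally, the study defines no single primary endpoint (4.2), tests no confirmatory hypothesis (11.1), and has no decision that rests on day-28 mass cytometry.

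Most of this stands as a limit on size. The averaged figures in step 4 are the fairer summary of the expected loss of precision. It does not close the gap: a dated line specific to vaccines implies that vaccination outside its window is allowed, and the undated line does not clearly override it. Section 8.6 shows that the sponsor wants a second allergen stimulus kept away until the day-28 draw; vaccines were not included in that rule. Recording a vaccine at Visit 5 also leaves open how that sample is to be shown.

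**Conclusion.** The concern holds as a minor, optional improvement. As written, the plan does not clearly exclude a vaccine in the 13 days before the day-28 blood draw. Under the assumed rates and shifts, the average cost is a 0.4-14% larger standard error for a day-28 between-arm comparison on a non-specific readout, with a larger distortion in the particular arm if a vaccine occurs. Vaccination is not expected to differ by arm, so no systematic bias is expected, although chance imbalance is possible with 15 per arm. Because 11.5 keeps all data, an affected sample would remain in the results. The text reading is firm; the size rests on a vaccination rate and an effect that the documents do not give.

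**What to change.** Change the limit in 7.1 to no vaccination from two weeks before the study injection until the day-28 blood draw. Repeat it in 8.6 beside the allergen-injection rule, which already runs to that draw. Ask specifically about planned vaccinations over that longer period at the screening visit.

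If a vaccine is medically needed, give it and record its date at the Visit 5 concomitant-medication check in Table 1. Keep the sample, consistent with 11.5, and mark it in the day-28 plots so that a reader can see which point it is.

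The cost is two wording changes and two more weeks without elective vaccination per patient; a few patients may have to reschedule. No visits, samples or patients are added.

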DSUR	Development safety update report
FNA	Fine needle aspiration
GCP	Good clinical practice
IB	Investigator's Brochure
Ho	Null hypothesis
HRA	Federal Act on Research involving Human Beings (in German: HFG, in French: LRH, in Italian: LRUM)
IEC	Independent Ethics Committee
IMP	Investigational Medicinal Product
IIT	Investigator-initiated Trial
ILIT	Intralymphatic immunotherapy
ITT	Intention to treat
PI	Principal Investigator
SCIT	Subcutaneous Immunotherapy
SDV	Source Data Verification
SmPc	Summary of Product Characteristics
SOP	Standard Operating Procedure
SPC	Summary of product characteristics
SUSAR	Suspected Unexpected Serious Adverse Reaction
TMF	Trial Master File
USZ	University Hospital Zurich

STUDY SCHEDULE

Table 1. Illustrating the study schedule with all interventions divided into the five visits. Patients will receive 6 SCIT injections as standard of care (not part of the study). 4-6 weeks later, the patients will be included in the clinical trials for assessment of immunological characteristics after a single ILIT or SCIT with subsequent fine needle aspiration (FNA), adverse event (AE) monitoring, and venous blood collection.

Visit / time point	1 Screening < 6 weeks of last SCIT	2 AIT	3 FNA	4 Follow-up	5 Follow up
		Day 0	Day 0-1	Day 7	Day 28
Required personnel	Nurse/MD	MD	MD	Nurse/MD	Nurse/MD
Informed consent	x				
Randomization	x				
Medical history	x				
Physical exam	x				
Incl./excl. criteria	x				
Blood samples		x	x	x	x
Pregnancy test		x			
AEs/Concomitant medication		x			x
Peakflow measurement		x*			
Injection: Study drug administration		x			
FNA (2x)			x**		
AE monitoring (1h observation at allergy unit after injection)		x			
Dispensing rescue medication		x			

* Peakflow measurement will be performed immediately before injection and 40 minutes after injection

** The FNA is performed 2, 6 or 24 hours after the Polvac™ ILIT or SCIT, and the injected (ILIT) or draining (SCIT) lymph node is used for FNA. For baseline reference, a contralateral lymph node is also aspirated.

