6. STUDY DESIGN

6.1 General study design and justification of design

This is a prospective, comparative, clinical open label pilot study. From patients with grass pollen allergy who undergo a pre-seasonal SCIT scheme with Polvac™ Grass+RyeSCIT at the USZ Allergy Unit, 30 patients will be recruited for the study that is illustrated in Figure 2.

Four to six weeks after end of SCIT treatment (at maximal maintenance dose), the patients will be randomized to one out of two treatment groups and receive one additional allergen injection. Fifteen patients will be allocated to receive another subcutaneous injection with 0.5 ml (2000 U) Polvac™

Grass+Rye. The other 15 patients will be allocated to receive an intralymphatic injection of 0.1 ml Polvac™ Grass+Rye with 400 U allergen. Both SCIT and ILIT injections are performed by ultrasound-guidance as to assure injection into the lymph node (ILIT) or 1 cm next to the lymph node (SCIT).

The FNA of lymph node tissue will be conducted at 2, 6 or 24 hours after allergen injection. At the same time, FNA of a contralateral lymph nodes will be performed as baseline. Venous blood will be sampled at all visits: at baseline as well as after 2, 6 or 24 hours, after 7 days and after 28 days of the allergen ILIT or SCIT. The FNA is performed by ultrasound-guidance.

[figure not shown]

Figure 2. Study design illustrated schematically the open-label clinical pilot study for assessment of immunological and inflammatory responses to a single ILIT or SCIT in patients receiving grass pollen immunotherapy with Polvac™ Grass+Rye.

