6.2 Methods of minimising bias

6.2.1 Randomisation

All patients who give consent for participation and who fulfil the inclusion criteria will be randomized to either SCIT or ILIT treatment group with a 1:1 allocation. The randomisation list will be computer-generated by a statistician using a permuted block design (groups of six). Before trial initiation, randomisation envelopes will be given to the study physician who will then be responsible of envelope storage and appropriate use. Allocation concealment will be ensured as the randomisation envelopes will not be opened before the patient has been recruited into the trial, which takes place after screening has been completed.

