9.2.4.3 Vital signs

A physical examination is done in a semi-structured way; several items are checked on a list in the CRF, and details can be entered if required.

The following vital signs will be assessed (e.g. heartbeat, lung auscultation and blood pressure).

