9.3 Procedures at each visit

9.3.1 Visit 1: Screening visit (20 minutes)

Completed until 02.02.2024 (-29 to 1 days before Visit 2)

- Interview with medical investigator
 - Medical history
 - Check of Inclusion/Exclusion criteria

- Physical examination
- Reading and signing of informed consent by participant and medical investigator

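### Table 1 allocates the arm at screening, before the injection-day exclusions and any ultrasound view of the nodes can be settled

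*Combined protocol and SAP*

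**What the plan says.** **Eligibility.** Section 7.1 lists "Conspicuous lymph node size or morphology" among the exclusions left to the recruiting physician's judgement. It names no size limit and no method of examination. The same section excludes infection at the treatment visit, an allergic reaction in the 4 days before the injection, anaphylaxis in the month before it, and vaccination within two weeks either side of it. Pregnancy is also an exclusion, and the test is done at Visit 2 (Table 1, 9.3.2).

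**Screening.** Section 7.2 describes "a screening visit 1 to 60 days before the intervention", at which all criteria are assessed, with "a short clinical exam (auscultation of the lungs and the heart, blood pressure measurement". Section 9.3.1 gives the interval as "29 to 1 days before Visit 2". Section 9.2.4.3 refers to a checklist in the CRF and adds: "The following vital signs will be assessed (e.g. heartbeat, lung auscultation and blood pressure".

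**Randomisation.** The Table 1 row reads "Randomization x", with its only mark under Visit 1. Section 6.2.1 says that "the randomisation envelopes will not be opened before the patient has been recruited into the trial, which takes place after screening has been completed". Section 6.1 says: "Four to six weeks after end of SCIT treatment (at maximal maintenance dose), the patients will be randomized". Section 8.1 also places randomisation four weeks after the SCIT cycle.

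**Ultrasound.** It is named for the injection (6.1, 8.2.1.1) and for the fine needle aspiration (6.1, 8.2.1.2), and not before.

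**Late ineligibility.** Section 7.4 lets the physician exclude a patient at discretion and allows replacement.

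**The concern.** Concealed randomisation protects a comparison only if the decision to keep a patient is made before the arm is known. Here some exclusions can be decided only on the day of injection, and one, a node that looks abnormal only on ultrasound, is first visible when the node is located for the injection. If the envelope was opened at Visit 1, those decisions are made with the arm known, in a trial without blinding (6.2.2).

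The node criterion leaves the most room for judgement. It has no threshold, and the lymph node is the tissue sampled for a primary outcome (5.1). ILIT puts allergen into the node and SCIT about 1 cm away, so a physician could reasonably weigh a borderline node differently by arm.

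Replacement restores the count but not the groups as randomised. Section 11.4 plans to test SCIT against ILIT, and neither 11.4 nor 11.5 defines an analysis set saying how a patient excluded after allocation is handled.

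**Working it through.** The plan has no figure to reproduce: 11.2 makes no sample size calculation, and no exclusion rate is given. The check is of the order of events, followed by two pieces of arithmetic.

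**1. Order if Table 1 is followed.** Visit 1: eligibility check, physical examination, randomisation. Visit 2: pregnancy test, first peak flow, baseline blood, ultrasound-guided injection. Visit 3: ultrasound-guided aspiration of the injected or draining node and of a contralateral node. The eligibility row of Table 1 is marked at Visit 1 only. Apart from the pregnancy test, the Visit 2 list in 9.3.2 has no eligibility check.

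**2. Order if 6.1 and 8.1 are followed.** Randomisation falls close to the injection, but neither section says what must be checked before the envelope is opened. The volume differs by arm (0.5 ml or 0.1 ml), and 8.1.3 has the syringe prepared at least 30 minutes before use. The arm is therefore known before the injection ultrasound unless a separate look is scheduled, and none is. The order of the other injection-day checks relative to allocation is left undetermined.

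**3. What Visit 1 can settle.** Let g be the days from Visit 1 to the injection, and w the look-back window before the injection. The days of the window still to come at Visit 1 are min(g, w). Inputs: g = 1 (shortest), 29 (9.3.1 maximum) and 60 (7.2 maximum); w from 7.1, with a month taken as 30 days.

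| Exclusion | w | g = 1 | g = 29 | g = 60 |
|---|---|---|---|---|
| Pregnancy test (Visit 2) | the day itself | open | open | open |
| Infection at treatment visit | the day itself | open | open | open |
| Allergic reaction | 4 days | 1 of 4 | 4 of 4 | 4 of 4 |
| Vaccination before injection | 14 days | 1 of 14 | 14 of 14 | 14 of 14 |
| Anaphylaxis | 30 days | 1 of 30 | 29 of 30 | 30 of 30 |

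At either maximum interval, none of these five can be settled at Visit 1. The two weeks without vaccination after the injection cannot be confirmed before allocation under any schedule.

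**4. Size.** One exclusion is 1/15 = 6.7% of an arm. For nodes visible only on ultrasound the documents give no rate p, so the following is for scale only. The expected number among 30 is 30p, and the chance of at least one is 1 − (1 − p)^30.

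| Assumed p | 30p | Chance of at least one |
|---|---|---|
| 1% | 0.3 | 26% |
| 2% | 0.6 | 45% |
| 5% | 1.5 | 79% |

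These are chances that the situation arises. They are not estimates of bias, and p may be near zero.

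**The case against.** The strongest reply has four parts.

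- **The node criterion is already applied before allocation.** Section 7.1 gives it to the recruiting physician, 7.2 assesses all criteria at screening, and 9.2.4.3 gives its examination items only as examples. This largely stands. A reader might infer that nodes are not examined at all before randomisation. The documents do not support that: the CRF checklist (Appendix 005) and Figure 4 are not available, so palpation cannot be ruled out. What remains is a node abnormal only on ultrasound, which palpation would not show.
- **The timing problem rests on one table mark.** Sections 6.1 and 8.1 put randomisation later, and 6.2.1 sets only an earliest moment for opening the envelope. This stands in part. A reader might infer that every patient is allocated up to 60 days before the injection, but that holds only if Table 1 is followed. Even so, the later reading requires no check before the envelope is opened.
- **Differential exclusion is not shown.** Nodes on both sides are needled for aspiration in both arms, so a suspicious node matters under SCIT too, and a pregnancy test or fever leaves little room for judgement. This stands. A reader might infer that the comparison is biased, but the documents show only that the order leaves this possible.
- **It is a descriptive pilot, and 7.4 already covers late ineligibility.** Section 11.1 does say that no hypothesis is being confirmed. But 4.2 makes the comparison of arms the primary objective, and 7.4 settles late ineligibility by discretion with the arm known, which is the difficulty rather than the answer to it.

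**Conclusion.** The point holds as a sequencing defect that should be corrected. As Table 1 is written, the arm is allocated before eligibility can be finally settled, and the text that places randomisation later does not require the final checks first. At least five exclusions tied to the injection or treatment visit are affected on the Table 1 reading. A node conspicuous only on ultrasound is affected on either reading.

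Each exclusion after allocation removes 6.7% of an arm. Their number is unknown and, for nodes, possibly close to zero. No direction or amount of bias can be derived from the documents. The conclusion assumes that Table 1 may be followed as marked and that the unavailable CRF and flow chart do not already schedule an ultrasound or an eligibility re-check before the envelope is opened.

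**What to change.** Move the randomisation mark in Table 1 to Visit 2. State in 6.2.1 and 9.3.2 that the envelope is opened only after two steps: the injection-day eligibility checks (pregnancy test, infection, recent allergic reaction, anaphylaxis, recent vaccination), and an ultrasound view of both groins, with the existing node criterion applied before the arm is known. Add no new eligibility criterion. This agrees with the timing in 6.1. An ultrasound at Visit 1 would deal with the node alone and leave the other exclusions open.

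No new equipment is needed. Ultrasound is already used at Visit 2, and the contralateral view is brought forward from the aspiration. Both arms use the same undiluted product (8.1.1), so the vial can be ordered and warmed before allocation. The study physician already holds the envelopes (6.2.1).

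The main cost is the wait while the arm-specific syringe is prepared. Section 8.1.3 gives a minimum of 30 minutes before use, which is 30/120 = 25% of the listed length of Visit 2 and at least 30 × 0.5 h = 15 patient-hours over the trial. The first peak flow and the baseline blood draw, already due before injection, can fill part of it. Some screen failures would fall on the injection day, and a warmed vial might then be wasted.
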